### 6.2.4 Additional Secondary Analyses

Both ICU and hospital length of stay will be compared using Wilcoxon Rank Sum tests. Ventilator and shock free days over the first 7-days after enrollment will likewise be compared using the Wilcoxon Rank Sum given that the data will likely be not normally distributed. In these latter two analyses, patients who expire prior to 7-days will be assessed to have 0 ventilator or shock free days if they had died while on a ventilator or vasopressor respectively. The incidence of delirium will be compared using the Fisher's exact test. For the quality-of-life outcome (i.e. 90-day SF-36), the primary analysis will only include patients with available data. As a secondary analysis, multiple imputation will be used to estimate SF-36 scores in all patients not known to be dead at 90 -days.

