## 5.3 Additional Secondary Outcomes

### 5.3.1 Additional secondary outcomes

Additional secondary outcomes will include length of ICU stay, length of hospital stay, ventilator-free days over the first 7-days after enrollment, shock-free days over the first 7-days after enrollment,

and the incidence of delirium on day #3 of the ICU stay (as assessed using the Confusion Assessment Method [CAM-ICU] system). Sites at which the CAM-ICU is performed daily as part of standard-of-care should assess whether delirium occurs on any day during the initial ICU stay. See Appendix #2.

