## 6. SAMPLE SIZE CALCULATION AND STATISTICAL ANALYSIS PLAN

### 6.1 Sample size calculation

The study has been powered to have at least 80% power for the primary outcome and all key secondary outcomes as follows:

**SOFA Score:** Based on preliminary data, we conservatively anticipate a decrease in SOFA score of 6 (standard deviation [SD]: 4) in the treatment group and 4 (SD: 2) in the placebo group. With these estimates, enrollment of **200 participants (100/arm)** at an alpha of 0.05 and using a t-test with unequal variance, the trial will provide > 99% power to detect a statistical significant difference between groups.

**Kidney Injury:** Based on preliminary data from our study of vitamin B1 in septic shock, we anticipate that 30% of participants in the treatment group and 55% in the placebo group will have renal failure which will result in a 94% power for this outcome. This calculation and following calculation were performed using the Fisher's exact test.

**Mortality:** Based on preliminary data, we anticipate that the control group will have a mortality of 40%. We estimate a treatment effect of 50% (risk ratio: 0.50) resulting in a mortality of 20% in the treatment group. With these estimates, 182 participants will lead to 80% power. To further increase

the trial's power and due to potential loss-to-follow-up, we will aim to enroll 200 participants. These estimates are conservative compared to the Marik et al. study which found a treatment effect corresponding to a risk ratio of 0.21 which persisted in adjusted analysis.

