## 6.2 Statistical analysis plan

### 6.2.1 General considerations

The statistical analyses and reporting will adhere to the CONSORT guidelines. All tests will be two-sided, a p-value  $< 0.05$  will be considered significant, and all confidence intervals will have 95% coverage. All analyses will be conducted on a modified intention-to-treat basis only including participants receiving at least the first dose of the study medications. In a double-blind trial, this approach is unbiased while increasing precision. The two groups will be compared in relation to baseline characteristics using descriptive statistics.

The persons conducting the statistical analysis will be blinded to the randomized allocation. Groups will be designated as "A" and "B" until all pre-specified analyses are performed and shared with all authors and the Data Safety Monitoring Board.

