### 7.2 Variables

Will be provided on the online CRF. A PDF version is available upon request.

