### **7.3 Data quality and validity**

Data quality and validity will be optimized by using a detailed data dictionary which will be distributed to all sites. Data quality will be monitored both centrally by the coordinating site and locally by each site principal investigator.

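### Section 6.2.4 does not say how deaths enter the ICU and hospital stay tests, so a survival benefit can read as a longer stay or hide a shorter one; the zero-free-days rule covers only deaths on support

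*Protocol*

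**What the plan says.** Section 5.3.1 lists the outcomes without defining them: "Additional secondary outcomes will include length of ICU stay, length of hospital stay, ventilator-free days over the first 7-days after enrollment", then shock-free days and delirium.

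Section 6.2.4 of the protocol sets the tests: "Both ICU and hospital length of stay will be compared using Wilcoxon Rank Sum tests". The free-day outcomes are also compared by Wilcoxon test. The section's only rule for deaths begins "In these latter two analyses, patients who expire prior to 7-days", which limits it to ventilator-free and shock-free days. Such participants score "0 ventilator or shock free days if they had died while on a ventilator or vasopressor respectively". The SAP's section 6.2.4 reads the same.

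Section 6.2.1 sets the population for all analyses as "only including participants receiving at least the first dose of the study medications", so participants who die are in the stay comparison. Section 6.1 says "we anticipate that the control group will have a mortality of 40" per cent, with 20% on treatment.

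Variable definitions are held outside the documents. Section 7.2 says of them "Will be provided on the online CRF. A PDF version is available upon request". Section 7.3 speaks of "using a detailed data dictionary which will be distributed to all sites".

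**The concern.** A Wilcoxon test needs a value for everyone. For a participant who dies in the unit, the obvious recorded value is the time to death. A death on day 2 then ranks among the best results. If placebo has twice as many deaths, more placebo stays are cut short, and saving lives makes the treated arm look slower to leave. If the drugs also speed recovery, as the before-after study in section 1.3 suggests, the two effects pull against each other and a real shortening can be missed.

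The silence is specific to stay: section 6.2.2 gives explicit death rules for SOFA and renal failure. Until a rule is fixed, the result depends on a choice that could be made after the data are seen.

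The free-day rule has a smaller gap. A participant off the ventilator at the end of day 2 who dies at the end of day 3 does not meet the condition for zero. The score is 1 if only days alive count and 5 if days after death count as free.

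**Working it through.** **The plan's figure.** For 40% vs 20%, two-sided 5%, 80% power:

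n = [1.96√(2 × 0.3 × 0.7) + 0.842√(0.24 + 0.16)]² / 0.2² = 1.802² / 0.04 ≈ 81.2 per arm.

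The continuity correction multiplies this by ¼[1 + √(1 + 4/(81.2 × 0.2))]² ≈ 1.12, giving 91 per arm, or 182 in total, as stated. Exact Fisher power is 80.8% at 91 per arm and 84.4% at 100. No figure in the plan is disputed; these are the death rates used below.

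**Inputs from the documents.** 100 per arm and 40% vs 20% mortality (6.1); two-sided 0.05 and all dosed participants (6.2.1).

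**Assumptions, because the documents give no timing.** All deaths occur during the stay. Time to death is exponential, mean 4 days (8 and 12 also tried). Survivors' stay is lognormal, median 7 or 14 days, log-SD 0.7. A death enters at its time of death.

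**Step 1: no effect on survivors' stay.** Let q be the chance that a survivor's stay exceeds a time to death, and pC and pT the mortality on placebo and treatment. The chance that a treated stay exceeds a placebo stay is

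θ = 0.5 + (pC − pT)(q − 0.5).

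So the shift vanishes if mortality is equal or if deaths and discharges have similar timing (q = 0.5). The Wilcoxon standard error for θ is √(201 / (12 × 100 × 100)) = 0.0409. With z = (θ − 0.5)/0.0409, the chance of a significantly longer stay is about 1 − Φ(1.96 − z).

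| Mean death 4 days | q | θ | z | Longer, formula | Longer, simulation |
|---|---|---|---|---|---|
| Median 7, 40% vs 20% | 0.783 | 0.557 | 1.38 | 28% | about 27% |
| Median 14, 40% vs 20% | 0.919 | 0.584 | 2.05 | 54% | about 55% |
| Median 7, 40% vs 30% | 0.783 | 0.528 | 0.69 | 10% | about 10% |
| Median 14, 40% vs 30% | 0.919 | 0.542 | 1.02 | 17% | about 17% |
| Equal mortality | any | 0.500 | 0 | 2.5% | about 2.5% |

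At 40% vs 20% with mean death 8 days, the simulated rates are 6% (median 7) and 28% (median 14); at 12 days, 2% and 13%.

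**Step 2: survivors' stay 25% shorter on treatment.** The chance that a treated survivor outstays a placebo survivor is a = Φ(ln 0.75 / (0.7√2)) = 0.386. Now

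θ = (1−pT)(1−pC)a + (1−pT)pC·qT + pT(1−pC)(1−qC) + 0.5·pT·pC.

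For median 7 and mean death 4 days, qT = 0.706 and qC = 0.783:

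- 40% vs 20%: 0.185 + 0.226 + 0.026 + 0.040 = 0.477, z = −0.56. A shorter stay is found in 8%.
- 30% in both arms: 0.189 + 0.148 + 0.046 + 0.045 = 0.428, z = −1.77. It is found in 42%.

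For median 14, the same comparison gives 1% against about 35%. For median 7 with mean death 12 days, it gives about 58% against 43%: the masking is gone.

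**Step 3: a different model.** With lognormal times to death (log-SD 0.8 for all times, survivor median 7), no effect on survivors' stay and 40% vs 20%, a falsely longer stay appears in 45%, 26%, 14% and 3% of trials at median times to death of 2, 3, 4 and 7 days. The pattern is the same.

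**Step 4: free days.** Assume survivors score 7 × Beta(2, 1.2), rounded, mean death is 4 days, and early deaths off support are free for a uniform share of their time alive. At 40% vs 20% a benefit is detected in about 54% of trials if every early death scores 0. With half of early deaths off support it is about 46% if only days alive count. If days after death counted as free, separate runs gave 7% to 14%.

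**The case against.** The strongest reply concerns size.

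- **The distortion needs a mortality difference.** The formula shows this, and the false-longer rate falls quickly below a halving of mortality. This stands in full.
- **A falsely longer stay is uncommon in the plan's hoped-for case.** If survivors' stay is 25% shorter, a significantly longer stay appears in only 0.7% (median 7) or 5.6% (median 14) at mean death 4 days. This also stands; in that case the problem is masking.
- **The timing is harsh.** An exponential time with mean 4 days puts 1 − e^(−1/4) = 22% of deaths in the first 24 hours, although anticipated death within 24 hours is an exclusion. Section 5.1.2 also provides for finding deaths after discharge. The largest percentages are therefore illustrations, not forecasts.
- **The data dictionary or CRF may define stay.** It may, and neither can be seen here. But how deaths enter a test is an analysis rule, and 6.2.4 is where a reader would look for it.
- **The free-day gap is small on the plain reading.** A reader might infer that a death off support earns credit for days after death. No section says so, and the large loss should not be attributed to the plan.
- **Any replacement also responds to mortality.** True: with no effect on survivors' stay and mean death 4 days, a competing-event analysis to day 30 favours treatment in about 58% of trials at 40% vs 20%. Its direction agrees with the benefit, however, and at 40% in both arms its total error stays near 5%.

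**Conclusion.** The omission is clear from the text. Stay is tested in all dosed participants with no rule for deaths, and the zero-free-days rule leaves out early deaths off support.

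The consequence is conditional. It requires that a stay ends at death, that mortality differs between arms, and that deaths come earlier than survivors' discharge. Under the plan's own mortality assumption and early deaths, the stay p-value can point the wrong way or miss a real shortening, at the rates shown above.

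A reader might infer that the stay test is biased whatever the drugs do, or that the trial's main conclusions are at risk. The documents support neither. At equal mortality the test keeps its nominal error. Only additional secondary outcomes are involved, and 30-day mortality is analysed separately in section 6.2.3, so unequal deaths will be visible. The correction should be made, but it does not bear on the primary analysis.

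**What to change.** Before unblinding, amend 6.2.4 in the protocol and SAP, and 5.3.1 to match:

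1. Every participant who dies before day 7 is assigned 0 ventilator-free and 0 shock-free days, whatever support was in use at death.
2. ICU and hospital stay are each analysed by one pre-specified method that does not treat death as a short stay. One suitable choice is time from enrollment to discharge alive, with death as a competing event, cumulative incidence curves and Gray's test, a stated horizon such as day 30, and participants who withdraw censored at withdrawal, since section 4.4.1 ends their data collection there.
3. Raw stay, and stay among those discharged alive, are reported by arm descriptively, without a test.

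The cost is wording. Death dates are already needed for the survival analysis and discharge dates for stay; sample size and conduct do not change. The definitions in 5.3.1 do change, because time to discharge alive is not length of stay. The tested measures then combine survival with duration, so a difference may mainly reflect mortality and must be read beside the 30-day mortality result. If bed use is the interest, the descriptive raw stay still shows it.

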### 6.2.5 Subgroup analyses

The analysis will include three pre-defined subgroup analyses for the primary and key secondary outcomes according to 1) participants with initially high SOFA scores ( $\geq 9$ ). This cut-off was chosen to represent a population with a  $\geq 50\%$  predicted likelihood of mortality 2) baseline vitamin B1 deficiency and 3) baseline adrenal insufficiency. We will not plan to perform a subgroup analysis according to vitamin C deficiency, as prior work has shown that the vast majority of participants with septic shock have vitamin C levels below the reference range. Vitamin B1 deficiency will be defined as a plasma vitamin B1 level  $\leq 7$  nmol/L as has been previously described. Adrenal insufficiency will be defined as a cortisol level  $< 10\mu\text{g/dL}$ . The trial is not powered to detect subgroup differences and these will be considered exploratory and hypothesis generating.

### 6.2.6 Statistical stopping criteria

Since the primary outcome is not mortality, there will be no formal stopping criteria for efficacy. There will be no predefined stopping criteria for futility since enrollment of the full cohort might allow for detection of efficacy in subgroups or in other outcomes even if the primary outcome is negative.

## 7. DATA COLLECTION AND MANAGEMENT

### 7.1 Data collection process

Data collection will be the responsibility of the individual site investigators with oversight from the trial coordinating center. Most variables (i.e. demographics, sepsis characteristics and laboratory results) will be obtained prospectively from the electronic medical record. 30-day follow-up regarding safety and mortality end-points will be obtained via telephone call post-discharge (unless the participant remains in the hospital at 30-days). Data will be entered directly into the online database software (see below).

### 7.2 Variables

Will be provided on the online CRF. A PDF version is available upon request.

### **7.3 Data quality and validity**

Data quality and validity will be optimized by using a detailed data dictionary which will be distributed to all sites. Data quality will be monitored both centrally by the coordinating site and locally by each site principal investigator.

### **7.4 Data storage and security**

The database application we will use is REDCap Cloud (<https://www.redcapcloud.com/>). REDCap Cloud is a professional database that provides a user-friendly interface. The REDCap Cloud data management system is secure, fully compliant with all regulatory guidelines, and includes a complete audit-trail for data entry validation. Through these mechanisms, as well as relevant training for all involved parties, participant confidentiality will be safeguarded. All members of the research team will be required to complete standardized training in REDCap cloud, which will be documented within the software.

The consent form and other trial documents for each participant will initially be stored in a secure, locked place at the individual sites. Participating sites will be responsible for maintaining their own trial documents and study materials (e.g. signed ICFs, site logs etc). Trial documents generated at the Coordinating Center will be maintained the Coordinating Center. Following completion of the trial, documents will be maintained for a period of at least 2-years at each site per FDA regulations (or longer depending on local IRB guidelines).

## **8. ETHICAL CONSIDERATIONS**

### **8.1 Risks and Benefits**

#### *8.1.1 Potential benefits*

**Potential Benefits to Individual Participant:** Assuming our hypothesis is correct and our results are comparable to those previously published, individual participants enrolled in our study and randomized to the treatment arm will benefit from a better trajectory of organ failure and improved mortality. As many participants who survive an initial episode of sepsis will have a future admission for sepsis, participants participating in this study but randomized to the placebo arm may see a future benefit from knowledge gained.

**Potential Benefits to Society:** Septic shock remains a highly morbid clinical condition for which there is no specific therapy. Our study, assuming our hypothesis is confirmed, will provide strong support for the widespread adoption of vitamin C, corticosteroids, and vitamin B1 for participants with septic shock. This, in turn, will significantly improve participant outcomes and reduce the global burden of death related to septic shock. Thus, even if participants are randomized to the placebo arm, their involvement with this study has tremendous potential benefits for society as whole. If vitamin C, corticosteroids, and vitamin B1 are found to be neutral or harmful (the latter being highly unlikely), society will benefit as the study will likely prevent the widespread dissemination of an ineffective medication combination.

#### *8.1.2 Potential harms*

##### **Study Drug**

Vitamin C – Ascorbic acid is a water-soluble essential vitamin that is safe even at high doses. Nevertheless, adverse effects related to high-dose ascorbic acid have been described. These adverse effects include diarrhea/abdominal bloating, increased oxalate excretion, iron overload in participants with hemochromatosis, and hemolysis in participants with G6PD deficiency. We exclude participants with known renal failure, known G6PD deficiency, or known hemochromatosis to limit these potential risks. We will additionally exclude participants with known allergy to ascorbic

acid. Ascorbic acid has additionally been used in at least 3 clinical trials in critically-ill populations without major associated adverse effect.

Hydrocortisone – Hydrocortisone is a well-established medication for the treatment of refractory shock in sepsis. Some studies (e.g. CORTICUS) have found an increased incidence of secondary infection in participants with septic shock who receive steroids. This finding has not been replicated in other large trials of corticosteroids for sepsis. Additional hypothetical risks to the administration of hydrocortisone to participants with septic shock (e.g. increased gastro-intestinal bleeding, muscle weakness, and delirium) have not been found in clinical trials of corticosteroids in sepsis. Finally, hydrocortisone may increase the risk of hyperglycemia and hyponatremia.

Hydrocortisone will not be tapered in this study as prior studies have shown benefit with corticosteroids in septic shock without a taper. In addition, a recent large trial of corticosteroids in septic shock (ADRENAL, NEJM 2018) randomized patients to 7-days of corticosteroids or placebo and did not include a taper. In that trial there was no reported difference in rates of recurrent shock.

Vitamin B1 – The only potential serious side effect that has been reported from vitamin B1 administration is an extremely rare anaphylactic reaction (1:250,000 cases) and this might not even be of issue with the current manufactured version of vitamin B1 in the United States. The risk of an anaphylactic reaction was associated with a vitamin complex dispensed in Europe, and whether vitamin B1 was the actual offending agent remains unknown; however, this 0.0004% theoretical chance of an adverse reaction is incredibly low. In a series of 989 participants in the United States who received intravenous vitamin B1, none had an anaphylactic reaction and the only reported side effects were minor consisting of transient local irritation or in one case pruritus (0.093%). Further safety data comes from the clinical use of intravenous vitamin B1 at our coordinating site. At Beth Israel Deaconess Medical Center (BIDMC, coordinating center) vitamin B1 is provided liberally for participants with nutritional deficiency – for example, BIDMC has administered intravenous vitamin B1 in over 8,000 separate participant encounters from 2002 until present. Despite this heavy usage, no adverse reactions were reported in any of the 8,000 participant encounters.

The combination of vitamin C, hydrocortisone and vitamin B1 – To date, the only study of the combination of vitamin C, hydrocortisone and vitamin B1 was the above referenced study by Marik et. al.

All procedures will take place at the study site. All research procedures and monitoring will be conducted by experienced personnel, and participants will be in the ICU given critical illness. This permits closer observation and more detailed monitoring by clinicians familiar with the care of participants experiencing and resuscitated from septic shock.

### **Blood Collection**

Most participants will have existing venous or arterial catheters in place and we will be able to collect blood from these ports, essentially eliminating the risks associated with blood collection. In the very rare case that a participant does not have an indwelling line, the risk of venipuncture is extremely low, and will not exceed the risk of clinical blood draws the participant will already be receiving.

### **Loss of Confidentiality**

All measures will be taken to ensure that no confidential information is released. All participant information will be stored in a password protected database to which only study investigators will

have access. Additionally, all hard copies of study data will be kept in a locked office accessible only to study investigators. Thus, the risk of loss of confidentiality is very low.

## **9. MONITORING**

### **9.1 Institutional Review Board (IRB)**

The study will be reviewed and approved by the IRB at each participating site.

### **9.2 Data Safety and Monitoring Board (DSMB)**

The DSMB will be responsible for safeguarding the interests of trial participants, assessing the safety and efficacy of the interventions during the trial, and for monitoring the overall conduct of the clinical trial. The DSMB will consist of three clinicians with critical care experience in the management of septic participants. An independent biostatistician/epidemiologist will prepare all DSMB reports. The DSMB members will be chosen such to avoid any financial or intellectual conflicts of interest. The DSMB will review deidentified data after every 50 participants are enrolled to assess for safety; unless there are group differences necessitating unblinding (as determined by the DSMB), the DSMB will be blinded to treatment groups. The trial will continue while the DSMB review data. After each review, the DSMB will create a short report to the steering committee with recommendations for continuation, modifications, or termination of the trial. Criteria for recommending termination will be at the discretion of the DSMB and there will be no formal statistical criteria for termination due to efficacy or safety. A detailed charter for the DSMB will be provided.

